4.3.10 Assessment of acceptability

Descriptive statistics will be used to summarise assessments of feasibility and acceptability in terms of recruitment (willingness to take part and eligibility) and drop-out. Where possible, reasons for drop-out at 12 months will be recorded. Additionally, as a check on acceptability of the prognostic tool, Research Assistants will check participants' responses on measures included in the tool for completeness at initial assessment and the subsample follow up. If any are non-complete, participants' reasons for refusing to complete them will be recorded.

4.3.11 Assessment of treatments received

We will utilise electronic case notes to document any treatments received during the study. These will be recorded by the Research Assistant at follow up. In addition the core service use form [83] will be completed at follow up assessments with the consenting subsample participants. This instrument was developed by health economists with experience of UK-based economic evaluations

and consists of 10 items such as medications received, community-based health appointments and Accident and Emergency visits.

4.3.12 Analysis

Predictive validity: Effect of applying the prognostic tool versus usual practice will be assessed in the analysis. Treatments received (e.g. number of sessions of cognitive therapy) will be added as covariates in the analysis. External validation of the model will be undertaken by evaluating the discrimination and the calibration of the model developed in Phase 2 in the cohort of patients collected in Phase 3. Calibration refers to how closely the probability of the event predicted by the model agrees with the observed probability. It will be assessed graphically [60] – if predicted and observed probabilities agree over the whole range of probabilities, the plot shows a 45° line. The discriminative ability of the model will be measured with the *c* index. The *c* index is similar to the area under the receiver operating characteristic curve for logistic models and is measured on a scale ranging from 0.5 (no better than chance) to 1 (perfect prediction)[62].

Acceptability: Descriptive statistics will be used to summarise recruitment and attrition. Reasons for non-completion of any measures will be recorded and summarised.

Controlling for treatment received: Treatments received (e.g. number of sessions of cognitive therapy) will be added as covariates in the analysis.

Exploratory cost-effectiveness analysis: We will explore the potential cost-effectiveness of the new prognostic tool compared to usual care (no prognostic tool) from the perspectives of the NHS and Social Care (costs) and service users (health benefits) over 1, 2 and 5 year time-horizons. The primary and sensitivity analyses will use a cost-effectiveness acceptability approach to estimate incremental cost-effectiveness ratios, probability the new prognostic tool is cost-effective and net benefit statistic and generate cost-effectiveness-acceptability curves (CEAC). The range of hypothetical willingness to pay thresholds (WTPT) to gain a unit of health benefit values for the analyses will be £0 to £30,000, with a mid-estimate of £15,000 for the main analyses [86, 87]. For the primary analysis, the measure of health benefit for the primary analysis will be the quality adjusted Life year (QALY) and direct costs of health and social care services will be estimated (primary, secondary and community physical and mental health care; social care). Sensitivity analyses will explore the impact of using (i) alternative measures of health benefit (ii) including indirect costs of lost productive activity in the cost estimates. Threshold and scenario analyses will be used to explore the minimum level of effectiveness the prognostic tool needs to achieve to be cost-effective.

A decision analytic model will be used for all the analyses. The decision model structure, assumptions and data estimates will be developed iteratively from the reviews and analyses in Phases 1, 2 and 3 and structured discussions with key stakeholders (service users and health care professionals) and the research team at Investigator and Project Steering Committee meetings and through established service user networks in Manchester, the North East and Birmingham (face validity) [88]. Two researchers (Health Economics Research Fellow and [name]) will independently build and populate the model (internal validity). Sections of the model will be used to predict events/health states, costs and QALYs observed in the prospective cohort study and published literature (external validity).

It is anticipated that a Markov cohort model [89] will be an appropriate vehicle to capture transition between at risk, treated health states and the longer term recovery/relapse cycle of psychosis. The model will synthesise data from several sources to estimate the probability, costs and health benefits of events/health states. These include the data collected in Phases 1-3 to estimate probability of transition between risk states, with and without the prognostic tool, the costs and health benefits of the different risk states with and without appropriate treatment, the costs and health benefits of recovery and relapse states for psychosis. Data from systematic reviews, meta-analysis and controlled trials will be preferred to data from other sources. Probabilistic sensitivity

analysis will be used to account for data uncertainty in all analyses. Structural uncertainty will be assessed in the sensitivity analyses, threshold and scenario analyses outlined above.

5. Research timetable

The overall project will be undertaken over 51 months (01/10/18 - 31/12/22).

Phase 1 (evidence synthesis) will be completed within 16 months (01/10/18 – 01/02/2020). Prior to the start of the project, we will continue to consolidate our collaborative network and invite principal investigators of relevant ARMS cohort studies to join this collaboration. Between 01/10/18 to 01/01/19 we will finalise our review protocols and literature searches to identify all relevant IPD sets. The retrieval and processing of IPD will be completed by 31/11/19. In parallel, we will conduct the systematic review of multivariable prognostic models in the ARMS group (completed by 31/12/2019) and the focused health economic review. Data-analysis will be completed in parallel with the Phase 2 analyses (01/12/19 – 31/03/20). The Phase 1 findings will be written-up for publication by the 31/06/2020. In terms of health economic analyses, development and validation of decision analytic model structure and assumptions will be completed by 31/03/20. Estimation and validation of probability, cost and health benefit variables, initial analyses and model verification will take place between 01/04/20 and 31/10/22.

Phase 2 (development of prognostic tool) will start on 01/12/19. By 31/03/20 we will complete (1) the statistical analyses updating, and if necessary developing and internally validating a novel prognostic model and (2) the focus groups to assess feasibility and acceptability of prognostic factors identified in the evidence synthesis – to be conducted between 01/12/19 and 28/2/20.

Phase 3 (cohort study) will be undertaken over 33 months (01/11/20 - 01/05/22), and will be preceded by a 3-month set up period (01/08/20 - 31/10/2020) for gaining all necessary ethics/research governance approvals and ensure the timely recruitment/training of the RAs at all sites. Recruitment will commence on 01/11/20 and continue for 18 months. 12 month follow-up assessments will commence on 01/11/2021 and completed by 01/05/22. Data analysis will commence on 01/05/23 and, as findings become available, we will start the write-up of reports, journal submissions and our planned dissemination activities.

Final health economic analysis will occur from 01/05/23 to 30/04/23. The final HTA report will be submitted on the 31/07/23.

6. Outputs

The project will lead to the following outputs:

- A refined prognostic tool suitable for use in the NHS that improves the prediction of development of psychosis over and above the existing ARMS criteria.
- A Risk Calculator website: The prognostic tool will be made free of charge to NHS clinicians working with ARMS individual via a website, hosted by an NHS Trust. The website will include the measures that have been externally validated as predictive of development of psychosis and will provide an individualised estimated risk level for based on scores for each measure inputted by the clinician. In this way, it will be similar to risk calculators such as the online QRisk calculator that estimates an individual's 10 year risk of a myocardial infarction or stroke according to their level of known risk factors (see https://qrisk.org/three/index.php). Unlike the QRisk calculator, we plan that our website will be password protected to help ensure that it is only accessed by service providers who will be able to interpret the results appropriately.
- A published IPD meta-analysis of prognostic factors associated with transition to psychosis in the ARMS group;
- A published systematic review of ARMS prognostic models;

- A refined prognostic model and tool, complemented by an online risk stratification calculator that will be accessible through an NHS-hosted website and suitable for immediate implementation at the end of the research;
- A training package that supports the use of the tool and website
- A published paper illustrating the validity and performance of the new prognostic tool in a large UK sample of ARMS individuals;
- A health economic model that will guide the implementation tool across NHS services, and will be published in a peer-reviewed journal.

7. Research management arrangements

Effective project management will be established and maintained throughout the project. The applicants will establish an effective system of support to ensure high quality research governance across all stages of the research, and that this project is undertaken in a timely and effective way.

Investigator Meetings: 5 meetings will be held in Year 1, the first a videoconference meeting of all investigators and then 4 meetings of investigators closely involved in the evidence synthesis (2 face to face, 2 by videoconference). In Years 2 - 5 there will be an all-investigator face to face meeting each year and videoconference meetings every 2 months to monitor progress.

We will also set up a Project Steering Committee (PSC) prior to the start of the study. The PSC will comprise the study applicants, representatives of service users and sponsor, and have an independent chairman. It will meet annually. The PSC will monitor and supervise progress, consider reports and recommendations and responsible for approving relevant protocols and standard operating procedures.

An Independent Data Monitoring and Ethics Committee (IDMC) will also be established prior to the start of Phase 3 to monitor (1) participant recruitment, (2) ethical issues of consent, (3) quality of data (4) the incidence of adverse events, and (5) any other factors that might compromise the progress and satisfactory completion of the project. This will also have an independent chairman, and include an independent statistician. It will meet 6-monthly during the cohort study.

Prior to the start of Phase 3, we will ensure researchers at all sites receive training in Good Clinical Practice. Each site will have a weekly team meeting and the Manchester-based project manager, who will conduct weekly telephone supervision with all RAs that will focus on recruitment, liaison with referrers, compliance to follow-ups, and scoring queries for assessment measures. Lead Applicant [name], who developed the CAARMS and associated training material, will provider regular monthly CAARMS supervision for Research Assistants and the Project manager and will be available for ad hoc scoring queries. She already provides monthly CAARMS supervision for Manchester-based clinicians and will extend this to other sites (via videoconferencing/ teleconference). These meetings will be supplemented by local supervision by site-PIs, focusing on problem solving and adherence to local policies and procedures.

8. Publication policy

In addition to the HTA report, the findings of this project will be published as series of papers in peer-reviewed journals. Group authorship on all outputs arising from the Phase 1 IPD meta-analysis will be offered to collaborators who will provide relevant IPD for the evidence synthesis conducted as part of this project.

9. Conflicts of interest

The applicants have no conflicts of interest to declare

10. Funding acknowledgement:

This project was funded by the NIHR Health Technology Assessment Programme (project number 17/31/05)

11. Department of Health disclaimer:

The views expressed are those of the authors and not necessarily those of the NHS, the NIHR or the Department of Health.

References

- 1. Global Burden of Disease Study, C., Global, regional, and national incidence, prevalence, and years lived with disability for 301 acute and chronic diseases and injuries in 188 countries, 1990-2013: a systematic analysis for the Global Burden of Disease Study 2013. Lancet, 2015. 386(9995): p. 743-800.
- 2. Häfner, H., et al., *The ABC schizophrenia study: a preliminary overview of the results.* Social Psychiatry and Psychiatric Epidemiology, 1998. 33(8): p. 380-386.
- 3. Schizophrenia Commission, *Schizophrenia The Abandoned Illness*, R. Murray, Editor 2012.
- 4. [name], A., et al., *Monitoring and care of young people at incipient risk of psychosis.* Schizophrenia Bulletin, 1996. 22(2): p. 283-303.

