4.3.6 Sampling

Consecutive sampling will be used.

Sample size: We aim to recruit 798 ARMS individuals over 18 months, with an anticipated attrition rate of 30% leaving a target follow-up of 558 participants at 12 months. Using an estimated 20% rate of development of psychosis ("transition rate") within 12 months we expect to see 112 cases of psychosis ("transitions"). A more conservative estimate would be 100 transitions (18% transition rate). This estimated transition rate is based on recent data of an over 25% rate in Early Intervention for Psychosis Services (EIPS) in both Manchester and Warwick. This rate, which is higher than those recently reported [76], is to be expected given the change in the way that many ARMS patients are now coming to clinical attention following implementation of the Access and Waiting Times Standard in Early Psychosis [11]. This Standard requires all individuals referred to EIPS in England to be assessed within 2 weeks. If they are found not to have a psychosis then they must be assessed for presence of an ARMS. This means that many ARMS individuals have high levels of symptoms (they were thought to actually have psychosis by referrers). This pathway is similar to the first ever ARMS service established in Melbourne by Lead Applicant [name]. This service (the PACE Clinic [36]) managed individuals who were referred to the EIPS but were found to be below threshold for psychosis. Reflecting this, the rate of development of psychosis in early studies was 35-41% within 12 months [5, 77].

Justification of Sample Size: We expect to see 100 - 112 transition events during the study. Latest research regarding sample size calculations for external validation studies suggests at least 100 events and 100 non-events to access calibration-in-the-large and calibration slope, and at least 200 events and 200 non-events to derive flexible calibration curves for logistic regression [78, 79]. This was demonstrated via assessment of multiple measures of calibration including the c-statistic, calibration-in-the-large, and calibration slope using five established simulated examples [80].

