4.3.9 Assessment of primary outcome

The primary outcome is development of psychosis by 12 month follow up. Psychosis onset will be assessed using the standard definition of psychosis included in the CAARMS. (This is essentially 7 days or more of full threshold psychotic symptoms occurring at least several times per week) or by clinician's notes on transition events which may include the following:

- Standard diagnostic classification systems (DSM-III, DSM-IV, DSM-5, ICD-10, ICD-11) or commonly used ARMS assessment schedules (e.g. SIPS or CAARMS)
- Standard treatment pathway decisions by clinicians- i.e. moved to a first episode psychosis treatment pathway
- A treated or untreated psychotic episode of one week's duration or longer;
- Treatment with antipsychotics at dose of over 5 mg of haloperidol or equivalent for over 3 weeks.

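### Section 4.3.12 adds treatments received during follow-up as covariates without keeping them out of the external validation, so the reported c index and calibration may not describe the baseline tool

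*Protocol*

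**What the plan says.** Under Predictive validity, section 4.3.12 first says that the effect of applying the tool versus usual practice will be assessed, and then: "Treatments received (e.g. number of sessions of cognitive therapy) will be added as covariates in the analysis". The next sentence says that external validation consists of "evaluating the discrimination and the calibration of the model developed in Phase 2 in the cohort of patients collected in Phase 3", with calibration judged graphically and discrimination by the c index. The covariate sentence appears again under its own heading, Controlling for treatment received.

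Section 4.3.11 defines what is collected: "We will utilise electronic case notes to document any treatments received during the study". The research assistant records it at follow-up. A service use form, which covers medications, is added in the consenting subsample. No cut-off at the date of transition is given.

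Section 4.3.9 lists evidence that may count as transition. It includes a move to a first-episode treatment pathway and "Treatment with antipsychotics at dose of over 5 mg of haloperidol or equivalent for over 3 weeks".

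Section 6 describes the finished tool as a calculator that returns a risk from the scores a clinician enters. Section 4.3.6 bases the sample size on calibration-in-the-large and calibration slope.

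**The concern.** External validation asks how predictions fixed in advance, from baseline information, perform in new patients. A covariate for treatment received during follow-up interferes with this in three ways.

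1. **It is not available at the time of use.** Section 2 envisages the tool guiding who is offered CBT and who is monitored. The number of sessions follows that decision, so a model containing it cannot be run at the point of use.
2. **It can be a consequence of the outcome.** Treatment is counted over the whole study. If transition shortens, lengthens or redirects therapy, the session count carries information about whether transition has happened.
3. **It can overlap with the outcome definition.** If medication or pathway is among the treatments entered, the covariate may partly restate what section 4.3.9 counts as transition.

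A covariate also needs a coefficient, and the tool supplies none for treatment. It would have to be estimated in the validation cohort, which can hide the miscalibration that validation is meant to reveal. At stake is the main result of Phase 3, whose stated aim (section 4.3.2) is the tool's external validity.

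**Working it through.** **Inputs from section 4.3.6.** "We aim to recruit 798 ARMS individuals over 18 months"; "anticipated attrition rate of 30% leaving a target follow-up of 558 participants at 12 months"; "within 12 months we expect to see 112 cases of psychosis" at a 20% rate, or 100 at 18%.

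**The plan's own figures reproduce.**
- Followed up: 798 × (1 − 0.30) = 558.6, stated as 558.
- Transitions: 558 × 0.20 = 111.6, stated as 112; 558 × 0.18 = 100.4, stated as 100.

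**Assumptions not in the protocol.** True c of the tool (0.70, with 0.65 and 0.50 also tried); uptake, frequency and timing of therapy; transition time uniform over the year.

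**Simulation with no treatment effect.** The outcome was generated from the baseline score alone. The c index of the unchanged score was compared with that of a logistic model refitted in the same cohort on score plus number of sessions. N = 558, 20% transition.

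Fortnightly sessions, true c 0.70, 400 cohorts:

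| Delivery pattern | c, score + sessions |
|---|---|
| Front-loaded 16-session course, 50% uptake | 0.707 |
| Sessions stop at transition, 50% uptake | 0.742 |
| Sessions stop at transition, 100% uptake | 0.918 |

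A repeat with 300 cohorts gave 0.709, 0.741 and 0.920.

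On average one session a month, everyone in therapy, 600 cohorts per pattern (1,000 for c = 0.50):

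| Delivery pattern | True c 0.70 | True c 0.65 | True c 0.50 |
|---|---|---|---|
| Sessions unrelated to outcome | 0.70 | 0.65 | 0.54 |
| 25% of those who transition stop therapy | 0.72 | 0.68 | 0.60 |
| Session rate doubles after transition | 0.86 | 0.84 | 0.82 |
| All who transition stop therapy | 0.88 | 0.87 | 0.86 |

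At 18% transition the results agree within 0.01. The rise from 0.50 to 0.54 in the first row is in-sample fitting alone.

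**Scale.** The sampling SD of c was about 0.03. In the fortnightly setting the shift is (0.707 − 0.70)/0.03 ≈ 0.2, (0.742 − 0.70)/0.03 ≈ 1.4 and (0.918 − 0.70)/0.03 ≈ 7 standard errors. The range therefore starts near zero.

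**Calibration after a full refit.** Let L be the fitted linear predictor and p = expit(L). Maximum likelihood with an intercept gives Σ(y − p) = 0, so calibration-in-the-large is 0. Each covariate gives Σx(y − p) = 0. L is a linear combination of the intercept and covariates, so ΣL(y − p) = 0, and regressing y on L in the same data returns slope 1. Both follow from the fitting, however badly the Phase 2 model is calibrated. If instead the Phase 2 linear predictor is held as an offset and only an intercept and treatment terms are estimated, calibration-in-the-large is still forced to 0, but the slope is not.

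**Simulation with a real treatment effect** (assumed odds ratio 0.9 per session, more sessions at higher risk, score built with true c 0.70). The unchanged tool had c 0.64 and slope 0.65. With sessions added, c was 0.66 and the score's coefficient 1.01. The adjusted model would not show that the tool is miscalibrated under current care.

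**The case against.** The strongest reply is that the treatment sentence does not govern the validation. It follows the sentence about the tool versus usual practice, so its analysis may be that comparison. The sentence after it says that the Phase 2 model itself will be evaluated, and the c index and calibration are described there. Objective 3b, the sample-size argument and the description of the calculator all fit a frozen model. The analysis plan, not available here, may settle the order of analyses.

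Much of this stands. A reader might infer that the protocol replaces validation of the frozen model with a refitted one, and that Phase 3 therefore cannot meet its aim. The text does not say so; it contains both statements and does not separate them.

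Two other inferences also fail:

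- **That the bias usually favours the tool.** Direction and size depend on delivery patterns that the protocol does not give. In the fortnightly no-effect simulations the score's own adjusted coefficient stayed at 1.01 to 1.02, so the inflated c belonged to the combined model.
- **That antipsychotics will be a covariate.** Therapy sessions are the only example named, and only antipsychotic treatment above a dose and duration threshold counts towards transition.

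The wish to account for treatment is also legitimate, since effective treatment can mask risk. What the reply leaves unanswered is that the covariate sentence sits under Predictive validity, is repeated, has no cut-off at transition, and is nowhere labelled secondary. An analyst following it literally would adjust the validation.

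**Conclusion.** The point holds as a defect in what the protocol fixes: the treatment covariates are not kept apart from the validation measures. If the c index and calibration are reported from a model containing them, they do not describe the baseline tool. After a full refit, the two measures on which section 4.3.6 relies cannot show miscalibration.

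With no treatment effect and an assumed true c of 0.70, the c index ranges from unchanged (0.70, or 0.71 with a front-loaded course), through 0.74 at 50% uptake with sessions stopping at transition, to about 0.9 in the extreme case of universal therapy all year. True c, uptake and delivery pattern are assumptions. Inflation is therefore a possibility that the wording leaves open, not a predicted result. The calibration result needs none of these assumptions, only that the model is refitted in the same data. What the authors intend cannot be settled from the protocol.

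**What to change.** Replace the two covariate sentences in section 4.3.12 with wording to this effect:

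- The primary validation computes each participant's risk from the frozen Phase 2 intercept and coefficients and baseline items only. The c index, calibration-in-the-large, slope and calibration plot are obtained without re-estimating the model and without treatment covariates.
- Treatments received are described by band of predicted risk.
- Any treatment-adjusted analysis is labelled secondary or exploratory, uses only treatment before transition (or status at baseline), and is not reported as the tool's performance.

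This changes wording in the protocol and analysis plan and leaves the sample size as it is. The primary validation needs no new data. The secondary analysis, if kept, needs treatment and transition dates to be extracted from the case notes already being reviewed.
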